Study Design	This is a multi-center, single arm, non-randomized, open-label study of ⁶⁴ Cu-labelled SAR-bisPSMA (⁶⁴ Cu-SAR-bisPSMA) administered to participants with biochemical recurrence of prostate cancer (PC) following definitive therapy. Participants who provide informed consent will undertake a screening visit(s) to determine their eligibility to participate in the study. The maximum Screening period for each participant is 28 days. After the Screening period, eligible participants will receive a single administration of ⁶⁴ Cu-SAR-bisPSMA on Day 0, followed by a positron emission tomography (PET)/computed tomography (CT) scan at 1 to 4 hours post dose (Day 0 scan) and at 24 hours post dose (Day 1 scan). Safety of ⁶⁴ Cu-SAR-bisPSMA will be assessed post dose, on Day 0, Day 1 and Day 7. Participants will then continue into the Follow-Up period to verify the ⁶⁴ Cu-SAR-bisPSMA PET/CT findings by histopathology, conventional imaging modalities that are routinely used in the diagnosis and staging of PC and prostate-specific antigen (PSA) levels. The maximum Follow-up period for each participant is 180 days. The ⁶⁴ Cu-SAR-bisPSMA PET/CT scans will be assessed against a composite Reference Standard. The composite Reference Standard will be determined by an independent, blinded, central expert panel and may consist of histopathology, conventional imaging modalities that are routinely used in the diagnosis and staging of PC And PET/CT findings will be assessed against a composite Reference Standard. The composite Reference Standard will be determined by an independent, blinded, central expert panel and may consist of histopathology, conventional imaging modalities that are routinely used in the diagnosis and staging of PC and PSA levels.
Primary Study Objectiv	res and Endpoints
To investigate the safet tolerability of ⁶⁴ Cu-SAI	Endpoint y and Incidence and severity of treatment-emergent AEs and z-bisPSMA. SAEs following the administration of ⁶⁴ Cu-SAR-bisPSMA.
To investigate the abilit SAR-bisPSMA PET/C detect recurrence of PC	• Participant-level CDR, defined as the proportion of TP participants on the Day 0 scan out of all participants with a Day 0 scan.

_		
	•	Participant-level CDR, defined as the proportion of TP participants on the Day 1 scan out of all participants with a Day 1 scan.
	•	Region-level PPV, defined as the proportion of TP regions on the Day 0 scan out of all positive regions on the Day 0 scan.
	•	Region-level PPV, defined as the proportion of TP regions on the Day 1 scan out of all positive regions on the Day 1 scan.

Abbreviations: AE= adverse event; CDR= correct detection rate; CT= Computed Tomography; PET= Positron Emission Tomography; PC= prostate cancer; PPV= positive predictive value; SAE= serious adverse event; TP= true positive

Objective	Endpoint
To investigate the biodistribution of ⁶⁴ Cu-SAR-bisPSMA.	Biodistribution of ⁶⁴ Cu-SAR-bisPSMA on the Day 0 and Day 1 scan:
	• Maximum and mean SUVs in lesion(s), visceral/soft tissue, bone.
	Lesion-to-background ratio.
To assess the participant-level PPV of ⁶⁴ Cu-SAR-bisPSMA PET/CT.	• Participant-level PPV, defined as the proportion of TP participants on the Day 0 scan out of all participants with a positive Day 0 scan.
	• Participant-level PPV, defined as the proportion of TP participants on the Day 1 scan out of all participants with a positive Day 1 scan.
To assess the participant-level DR of ⁶⁴ Cu-SAR-bisPSMA PET/CT.	• Participant-level DR, defined as the proportion of participants with a positive Day 0 scan out of all participants with a Day 0 scan.
	• Participant-level DR, defined as the proportion of participants with a positive Day 1 scan out of all participants with a Day 1 scan.
To assess the FPR ⁶⁴ Cu-SAR- bisPSMA PET/CT.	• Participant-level FPR, defined as the proportion of FP participants on the Day 0 scan out of all participants with a positive Day 0 scan.
	• Participant-level FPR, defined as the proportion of FP participants on the Day 1 scan out of all participants with a positive Day 1 scan.
	• Region-level FPR, defined as the proportion of FP regions on the Day 0 scan out of all positive regions on the Day 0 scan.
	• Region-level FPR, defined as the proportion of FP regions on the Day 1 scan out of all positive regions on the Day 1 scan.

To assess the discrepant PET negativity rate of the ⁶⁴ Cu-SAR-bisPSMA PET/CT scans.	Participant-level discrepant PET negativity rate, defined as the proportion of participants with contradicting Day 0 and Day 1 results for whom the Reference Standard was positive.
To assess the TNR of ⁶⁴ Cu-SAR- bisPSMA PET/CT.	• Participant-level TNR, defined as the proportion of TN participants on the Day 0 scan out of all participants with a negative Day 0 scan.
	• Participant-level TNR, defined as the proportion of TN participants on the Day 1 scan out of all participants with a negative Day 1 scan.
	• Region-level TNR, defined as the proportion of TN regions on the Day 0 scan out of all negative regions on the Day 0 scan.
	• Region-level TNR, defined as the proportion of TN regions on the Day 1 scan out of all negative regions on the Day 1 scan.

Abbreviations: CT= computed tomography; DR= detection rate; FP= false positive; FPR= rate of false positive; PET= positron emission tomography; PPV= positive predictive value; SUV= standardized uptake value; TN= true negative; TNR= rate of true negative; TP= true positive

Exploratory Study Objectives and En	ndpoints
Objective	Endpoint
To evaluate the reproducibility of the ⁶⁴ Cu-SAR-bisPSMA PET/CT readings and consistency among readers.	Intra-reader variability per reader.Inter-reader variability expressed by kappa statistics.
To assess the impact of ⁶⁴ Cu-SAR- bisPSMA PET/CT on disease management.	Proportion of participants with any change in intended PC treatment due to either the Day 0 or Day 1 scan.
Composite performance of the Day 0 and Day 1 ⁶⁴ Cu-SAR-bisPSMA PET/CT scans.	• Composite CDR defined as the proportion of TP participants on the Day 0 and/or Day 1 scan out of all participants with a Day 0 and/or Day 1 scan.
	• Composite participant/region-level PPV defined as the proportion of TP participants/regions on the Day 0 and/or Day 1 scan out of all participants/regions with a positive Day 0 and/or Day 1 scan.
	• Composite DR defined as the proportion of participants with a positive Day 0 and/or Day 1 scan out of all participants with a Day 0 and/or Day 1 scan.
To determine the effect of baseline variables on the CDR, PPV and DR of ⁶⁴ Cu-SAR-bisPSMA PET/CT.	CDR, participant- and region-level PPV and DR of the Day 0 and/or Day 1 scan as a function of baseline variables.
To explore the correlation between ⁶⁴ Cu-SAR-bisPSMA PET-positivity and Reference Standard results.	Relationship between PET-positivity (biodistribution measures such as SUVs and lesion-to-background ratio), versus true/false positivity and as a function of lesion location and size.

To assess the performance of ⁶⁴ Cu-SA PET/CT.	 lesion-level Difference in the number of lesions detected per participant on the Day 0 versus the Day 1 scan. Overall agreement rate on the Day 0 and Day 1 scans, defined as the number lesions with matching subregion divided by the total number of lesions identified across all scans by either imaging. Overall agreement rate on the Day 0 and reference scans, defined as the number lesions with matching subregion divided by the total number of lesions identified across all scans by either imaging. Overall agreement rate on the Day 0 and reference scans, defined as the number lesions with matching subregion divided by the total number of lesions identified across all scans by either imaging. Overall agreement rate on the Day 1 and reference scans, defined as the number lesions with matching
	subregion divided by the total number of lesions identified across all scans by either imaging.
Abbreviations: CDR= corr cancer; PET= positron emis	ect detection rate; CT= computed tomography; DR= detection rate; PC= prostate ssion tomography; PPV= positive predictive value; TP = true positive
Number of	50
Participants Planned	
Target Population	The target study population is patients with biochemical recurrence of PC and negative or equivocal findings per institutional standard of care (SOC) conventional imaging.
Inclusion Criteria	Study candidates must meet all the following criteria to be eligible for the study:
	1. At least 18 years of age.
	 Signed informed consent.
	3. Life expectancy ≥ 12 weeks as determined by the Investigator.
	4. Histologically confirmed adenocarcinoma of prostate per original diagnosis and completed subsequent definitive therapy.
	5. Suspected recurrence of PC based on rising PSA after definitive therapy on the basis of:
	a. Post-radical prostatectomy: Detectable or rising PSA that is \geq 0.2 ng/mL with a confirmatory PSA \geq 0.2 ng/mL (per American Urological Association recommendation) or
	b. Post-radiation therapy, cryotherapy, or brachytherapy: Increase in PSA level that is elevated by ≥ 2 ng/mL above the nadir (per American Society for Therapeutic Radiology and Oncology-Phoenix consensus definition).
	6. Negative or equivocal findings for PC on conventional imaging performed as part of SOC workup within 60 days prior to Day 0.
	7. The Eastern Cooperative Oncology performance status 0-2.
	8. Adequate recovery from acute toxic effects of any prior therapy.
	9. Estimated Glomerular Filtration Rate of 30 mL/min or higher.
	10. Adequate liver function defined as alanine aminotransferase/ aspartate aminotransferase <3 x upper limit of normal (ULN) and

	total bilirubin <1.5 x ULN (except in the case of Gilbert's syndrome).	
	11. For participants who have partners of childbearing potential: Partner and/or participant must use a method of birth control with adequate barrier protection.	
Exclusion Criteria	Study candidates who meet any of the following criteria are not to be enrolled in the study:	
	1. Participants who received other investigational agents within 28 days prior to Day 0.	
	2. Participants administered any high energy (>300 keV) gamma- emitting radioisotope within 5 physical half-lives prior to Day 0.	
	3. Ongoing treatment or treatment within 90 days of Day 0 with any systemic therapy (e.g. androgen-deprivation therapy, antiandrogen, gonadotropin-releasing hormone, luteinizing hormone-releasing hormone agonist or antagonist) for PC.	
	4. Known or expected hypersensitivity to ⁶⁴ Cu-SAR-bisPSMA or any of its components.	
	5. Any serious medical condition or extenuating circumstance which the investigator feels may interfere with the procedures or evaluations of the study.	
Investigational Product, Dose, and	The investigational product administered in this study ⁶⁴ Cu-SAR-bisPSMA.	
Regimen	⁶⁴ Cu-SAR-bisPSMA has three basic components: (a) the radionuclide (⁶⁴ Cu) chelated by (b) bisCOSAR (a bifunctional metal chelator) which is linked to (c) two urea based small molecule inhibitors of Prostate Specific Membrane Antigen.	
	200 MBq of ⁶⁴ Cu-SAR-bisPSMA will be administered as a bolus intravenous injection at Day 0.	
Statistical Methods	A Statistical Analysis Plan (SAP) will be written after finalizing the protocol and prior to database lock. The SAP will detail the implementation of all the planned statistical analysis in accordance with the principal features stated in the protocol.	

TABLE OF CONTENTS

SPONSOR PROTOCOL APPROVAL	3
PROTOCOL SYNOPSIS	4
TABLE OF CONTENTS	9
List of Tables	12
LIST OF ABBREVIATIONS AND DEFINITIONS OF TERMS	
AMENDMENT 1 (1/2 0 10 EED 2022)	15
AMENDMENT 1 (V 2.0, 10-FED-2022)	13
AMENDMENT 1.1 (V2.1, 17-FEB-2022)	16
AMENDMENT 2 (V3.0, 07-DEC-2022)	17

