4.1.2 Exclusion Criteria

Study candidates who meet any of the following criteria are not to be enrolled in the study:

- 1. Participants who received other investigational agents within 28 days prior to Day 0.
- 2. Participants administered any high energy (>300 keV) gamma-emitting radioisotope within 5 physical half-lives prior to Day 0.
- 3. Ongoing treatment or treatment within 90 days of Day 0 with any systemic therapy (e.g. ADT, antiandrogen, gonadotropin-releasing hormone, luteinizing hormone-releasing hormone agonist or antagonist) for PC.
- 4. Known or expected hypersensitivity to ⁶⁴Cu-SAR-bisPSMA or any of its components.
- 5. Any serious medical condition or extenuating circumstance which the investigator feels may interfere with the procedures or evaluations of the study.

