7.1.2 Medical and Medication History

Medical history will include evaluation for relevant past or present diseases or disorders, and relevant surgical history.

Medication history includes any medication or vaccine (including over the counter or prescription medicines, vitamins, and/or herbal supplements) that the participant has received within 14 days before signing informed consent must be recorded on the eCRF along with:

- Reason for use;
- Dates of administration including start and end dates;
- Dosage information including dose and frequency.

7.1.3 **Prior Cancer Treatments**

As part of Screening, review of prior PC treatments received from the time of diagnosis will be completed and recorded on the eCRF. This must include type and date of the initial definitive treatment modality (e.g., radical prostatectomy, radiation therapy, cryotherapy, or brachytherapy).

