## 7.6 Calculation of PSA Doubling Time and PSA Velocity

The following values of PSA are collecting for this study:

- PSA at Initial Diagnosis
- Nadir PSA after initial definitive treatment
- Most Recent PSA prior to screening #1 and #2
- Screening PSA
- PSA taken during the study at day 90 and 180 (if appliable) or after start of salvage focal therapy (can vary)

PSA doubling time (PSADT) and PSA velocity will be calculated at baseline and during the study and require different definitions. PSA at initial diagnosis will not be used for any calculations of PSA velocity or PSADT.

For calculation of PSADT and PSA velocity at **Baseline**, which will be calculated for all participants:

- PSA Velocity = Slope of the line of best fit using all available data within 12 months prior to screening as well as screening value (excluding at initial diagnosis).
- PSADT = ln(2) / ((ln(PSA value at screening) ln(oldest PSA value within 12 months prior to screening)) / (# of months from oldest PSA value within 12 months prior to PSA at screening))

September 4, 2024 CONFIDENTIAL Page 18 of 46

For calculation of PSADT and PSA velocity for on-study measurements, only the last measure of PSA taken during the study will be used. The following calculations will be done for PSA measurements **Post-Baseline**:

- PSA Velocity = Slope of the line of best fit using all available data on-study, including screening value.
  - o If the participant initiated radiation therapy on-study, the last PSA value is instead the last PSA value PRIOR to initiating radiation therapy.
- PSADT = ln(2) / ((ln(Last on-study PSA value) ln(PSA at screening)) / (# of months from last on-study PSA value to PSA at screening))
  - o If the participant initiated radiation therapy on-study, the last PSA value is instead the last PSA value PRIOR to initiating radiation therapy.
- If a participant has no post-screening value prior to initiation of radiation therapy, they will be excluded from post-baseline calculations of PSADT and PSA velocity.

For the calculation of the line of best fit for PSA Velocity, the following equations will be used for each participant, where  $x_i$  is the date of the measurement in months from screening (screening is x = 0) for each value,  $y_i$  is the PSA value, and n is the total number of datapoints for the participant for that calculation:

$$\overline{X} = \frac{\sum_{i=1}^{n} x_i}{n} \quad \overline{Y} = \frac{\sum_{i=1}^{n} y_i}{n}$$

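### Baseline PSA doubling time can start from a PSA taken on androgen deprivation, because SAP 7.6 puts no treatment-date condition on its 12-month look-back

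*Protocol*

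**What the plan says.** Protocol 4.1.2 (and the Synopsis), exclusion criterion 3, rules out "Ongoing treatment or treatment within 90 days of Day 0 with any systemic therapy", with androgen deprivation among the examples. Systemic therapy that ended earlier than that does not exclude a man.

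SAP 7.6 defines baseline PSADT, "which will be calculated for all participants", as a two-point measure. It runs from the "oldest PSA value within 12 months prior to screening" to the screening value. Baseline velocity is the "Slope of the line of best fit using all available data within 12 months prior to screening as well as screening value". The only PSA removed from these calculations is the one at initial diagnosis. The remaining pre-screening values collected are the nadir after definitive treatment and the two most recent measurements (Protocol 7.2.7, SAP 7.6).

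The only treatment rule in SAP 7.6 applies after baseline and names radiation: "If the participant initiated radiation therapy on-study, the last PSA value is instead the last PSA value PRIOR to initiating radiation therapy".

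SAP 9.14.3.2 tabulates CDR, PPV and DR by baseline PSADT in four bins (<3.0, 3.0-8.9, 9.0-14.9 and ≥15.0 months) and by baseline velocity. SAP 9.14.3.6 summarises PSADT and velocity with change from baseline, overall and in subgroups that include TP, FP and TN participants.

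**The concern.** The eligibility window and the look-back window have different lengths. Criterion 3 clears systemic therapy from the 90 days before Day 0, while PSADT reaches back 12 months before screening. A PSA drawn during androgen deprivation can fall in the part of the look-back that criterion 3 does not cover. If it is the oldest value there, the formula starts from a suppressed level and attributes the whole later rise to tumour growth.

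The SAP accepts the principle after baseline, where it stops using PSA once radiation begins. It has no counterpart for the baseline look-back, and its table of deviations from protocol analyses (Section 8.0) does not present this as a deliberate choice.

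At stake is the reading of two exploratory outputs. Misplaced men would blur any relation between PSADT and detection in 9.14.3.2. A baseline PSADT that is too short would make a later PSADT look like slowing in 9.14.3.6.

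**Working it through.** The plan states no figure on this point, so there is none to reproduce. The check compares the windows and then applies the SAP formula.

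**1. Can an on-therapy value be the starting point?**
- Criterion 3 covers the 90 days before Day 0 only.
- SAP 7.6 takes the oldest PSA in the 12 months before screening and removes only the diagnosis value.
- Inclusion criterion 5 requires a PSA rise or a confirmatory value. It does not restrict the oldest value in the look-back.
- The eligibility criteria set no testosterone threshold.
- SAP 7.2 keeps results reported as below a limit at their numeric part, so an undetectable on-therapy PSA is not dropped.

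Nothing in the documents prevents it.

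**2. Formula (SAP 7.6).** With m months between the two values:

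PSADT = m × ln 2 / [ln(PSA at screening) − ln(oldest PSA)]

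**3. Illustration. All PSA values are assumed.** PSA is 0.05 ng/mL on therapy at −10 months, 0.5 off therapy at −3 months, and 0.7 at screening. Therapy is assumed to end between the first two values. The −3 month value lies about 91 to 119 days before Day 0 (3 months ≈ 91 days, plus 0 to 28 days of screening), so calling it off therapy requires that therapy stopped before then.
- SAP rule: 10 × ln 2 / ln(0.7/0.05) = 2.63 months (bin <3.0).
- Off-therapy values only: 3 × ln 2 / ln(0.7/0.5) = 6.18 months (bin 3.0-8.9).

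**4. Sensitivity to the on-therapy PSA**, all else as in step 3:

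| On-therapy PSA (ng/mL) | SAP PSADT (months) | Bin |
|---|---|---|
| 0.02 | 1.95 | <3.0 |
| 0.05 | 2.63 | <3.0 |
| 0.10 | 3.56 | 3.0-8.9 |
| 0.20 | 5.53 | 3.0-8.9 |

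Every result is shorter than 6.18 months. The bin changes only when the on-therapy PSA is below 0.7 / 2^(10/3) = 0.069 ng/mL.

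**5. Direction in general.** Let the true doubling time be T, let the oldest PSA be suppressed to a fraction f of its untreated value, and let suppression be gone by screening. Then

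observed PSADT = m × ln 2 / [m × ln 2 / T + ln(1/f)]

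This is below T for every f < 1. With T = 12 and m = 9 (assumed), f = 0.5, 0.2 and 0.1 give 5.1, 2.9 and 2.2 months. If both values are unsuppressed, ln(1/f) = 0 and the formula returns T.

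**6. Velocity** (least-squares slope per month × 12):
- Step 3 values: 0.78 ng/mL/y with all three points, against (0.7 − 0.5)/3 × 12 = 0.80 off therapy.
- Second example (assumed): screening PSA 0.5, T = 12, values at −9, −3 and 0 months, the first at f = 0.1. The slope is 0.65, against 0.27 ng/mL/y unsuppressed.

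All four results fall in the top bin of 9.14.3.2, ≥0.20 ng/mL/y.

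**The case against.** The strongest case on the other side is that little depends on this. Baseline PSADT feeds only exploratory stratification and descriptive PSA summaries, SAP 4.1 plans no formal hypothesis testing, and about 50 men spread over four bins and three readers give descriptive tables at best. Affected men can also be found in the listings, since SAP 9.9 lists therapies with start and stop dates and 9.14.3.6 lists every PSADT. This stands as a limit on importance. It does not correct the derived value.

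Three stronger readings are tempting, and the documents do not support them.

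- A reader might infer that most baseline values are exposed, because (365 + 0 − 90)/365 = 75% to (365 + 28 − 90)/365 = 83% of the look-back lies outside the washout. That is a share of calendar days, not of PSA values. Apart from the diagnosis value, only the nadir and the two most recent values are collected before screening, and an on-therapy PSA matters for PSADT only if it is the oldest of these in the window.
- A reader might infer that recently treated men land in the fastest bin whatever their tumour kinetics. Step 4 shows otherwise: on-therapy values of 0.10 and 0.20 leave the man in the bin he would have had anyway. Step 5 gives larger shifts, but only under assumed T, f and m.
- A reader might take the testosterone category below 230 ng/dl in 9.14.3.2 as a sign that recently androgen-deprived men are expected. It is only a category limit.

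It is also fair to say that filtering on the date of last therapy does not fully cure the problem, because a PSA drawn soon afterwards may still be suppressed or recovering. That stands, and is why the fix adds a flag.

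**Conclusion.** The point holds for PSADT. Under SAP 7.6 an eligible man can have a baseline PSADT that starts from an on-therapy PSA. If that value is suppressed and the suppression has lifted by screening, the result is biased short. The illustration gives 2.6 against 6.2 months and rests on assumed PSA values and an assumed stop date. The documents give neither the number of men with systemic therapy in the look-back nor their PSA values, so the effect in this trial is unknown and may be nil.

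The effect reaches only the tables by baseline PSADT in 9.14.3.2 and the PSADT change summaries in 9.14.3.6. CDR and PPV as co-primary endpoints, and the sample size, do not use PSADT. For velocity, the examples show no change of bin, so no material effect on those bins is claimed. Exclusion criterion 3 is not itself in error; the gap is in the SAP derivation.

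**What to change.** In SAP 7.6, for baseline PSADT, and for velocity so that the two measures use the same values:

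1. Use only PSA values dated after the end of the last systemic therapy recorded on the Prior Cancer Treatments eCRF. Men with no systemic therapy in the window keep the present rule. The data source exists: Protocol 7.1.3 says "review of prior PC treatments received from the time of diagnosis will be completed and recorded on the eCRF".
2. If fewer than two such values remain, screening included, set the measure to not evaluable and show these men as a separate row in the 9.14.3.2 tables.
3. Flag men with systemic therapy in the look-back window in the listings, because early post-therapy values may still reflect recovery.

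The cost is a few sentences of SAP text, a date filter in the derivation, one table row and one listing flag. The downside is that a few men will have no baseline PSADT or velocity. Eligibility is not changed.
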